2.2 Longitudinal Model

The primary endpoint is defined as the average change from baseline across measurements taken at 1, 4, 8, and 12 weeks. As patients complete follow-up visits, we gain knowledge of their final primary endpoint value. First, the change from baseline at an earlier visit is likely correlated with the change from baseline at a later time point. Additionally, as patients complete follow-up visits, we gain partial knowledge of their final primary endpoint value. For example, a patient who has completed 1, 4 and 8 weeks has an average change from baseline through 8 weeks and this value will be highly associated with the primary endpoint yet to be observed that will be inclusive of the last 12 week visit. The trial design makes use of a longitudinal model to allow the unobserved final endpoint value to be imputed from the partial primary endpoint value observed for those subjects that have not yet been observed through the 12-week visit.

Let Y_i be the final endpoint value through the 12 week visit for subject i . Let y_{it} be the intermediate endpoint value at visit t . Longitudinally, y_{it} could be defined in one of two ways. The y_{it} could be defined as the change from baseline to an intermediate visit t . The longitudinal model could be used to impute the y_{it} for all visits and then determine Y_i as the average of all y_{it} . Alternatively, y_{it} could be defined as the

Trial Code: 000233

average mean change from baseline inclusive of all measurements obtained through visit t . The last observed y_{it} could be used to impute unknown Y_i .

We consider that the y_{it} follow the latter definition, and are the average mean change from baseline inclusive of all measurements obtained through visit t . We use the last observed y_{it} to impute the final Y_i value for patients who have not yet completed the 12 weeks of follow-up. The dose-response model is then fit on the Y_i values across all enrolled patients. The dose-response modeling is described in Section 2.1. Missing intermediate endpoint values are expected to be rare and will not be imputed. The average at each visit will be computed among only observed completed intermediate visits.

The time course hierarchical model uses the observed average change through visit t to predict the final endpoint value Y_i . The observed average change at the t th visit for the i th subject on dose d is modeled as:

$$y_{it} \sim e^{\gamma_t} (\mu_d + \delta_i) + N(0, \lambda_t^2)$$

The imputed final response (visit T) for the i th subject is modeled as:

$$Y_i \sim \mu_d + \delta_i + N(0, \lambda_T^2)$$

that is, with γ_T equal to 0. Thus, the model has components for

- the per subject difference in response (δ_i) from the mean dose response (μ_d),
- the error as a function of knowing the i th value is modeled, $N(0, \lambda_T^2)$

The prior distributions are:

$$\gamma_t \sim N(\mu_\gamma, \sigma_\gamma^2)$$

$$\delta_i \sim N(0, \tau_i^2)$$

$$\tau_i^2 \sim IG(a_\tau, b_\tau)$$

$$\lambda_t^2 \sim IG(a_\lambda, b_\lambda)$$

We define 3 separate model instance for correlating the averages observed at earlier visits to the final primary endpoint value. The control, active comparator, and 6 active doses of FE 201836 are modeled with separate model instances. Each model instance will be fit using only the data from the arm(s) it corresponds to. All model instances are identical and we use the same priors for all instances. The priors are

Trial Code: 000233

$$\tau_f^2 \sim IG(0.5, 0.36125)$$

$$\lambda_f^2 \sim IG(0.5, 0.125)$$

The priors for the longitudinal model parameter γ_t are show in Table 1.

Table 1: Prior parameters for longitudinal model parameter γ_t

	μ_γ	σ_γ^2
Week 1 to Week 12	0	1
Week 4 to Week 12	0	1
Week 8 to Week 12	0	1

2.3 Evaluation of Posterior Estimates

The Bayesian model fitted to the data at each update contains a final endpoint dose-response model and a longitudinal model used for imputing the final mean change from baseline. The posterior distribution for the dose-response parameters is calculated as follows.

1. A longitudinal model is created to link all the visit integrated mean changes from baseline observations to the final integrated mean change over the visits. We label the model as

$$g(y_{it}|\gamma, \delta, \mu, \lambda) \sim e^{\gamma t}(\mu_d + \delta_i) + N(0, \lambda_f^2) \quad t=1,2,3,4$$

2. We created a dose-response model for the inference of the dose-response parameters given the final visit mean integrated change from baseline, y_i (the mean change from baseline of the four visits, which is y_{i4})

$$f(y_i|\alpha, \sigma) \sim \alpha_1 + \frac{(\alpha_2 - \alpha_1)v_{d_1}^{\alpha_4}}{v_{d_1}^{\alpha_4} + \alpha_3} + N(0, \sigma^2) \quad i=1, \dots, n$$

The posterior distribution of the dose-response parameters is calculated using Markov chain Monte Carlo simulation. In the algorithm the following steps are taken

- A. An observation of the parameters of the longitudinal model ($\gamma, \delta, \mu, \lambda$) are drawn from their complete conditionals.
- B. An observation for the final mean integrated change from baseline for each subject with incomplete data is imputed from $g(y_{it}|\gamma, \delta, \mu, \lambda)$ conditional on the draws from A.
- C. An observation from the complete conditional distribution of the parameters

Trial Code: 000233

of the dose-response model (α, σ) is drawn given the complete data imputed in B and the naturally completed data in the trial.

- D. Any posterior distribution summaries are tabulated from the draws in C that are past the burn-in period of the MCMC algorithm.
- E. Repeat A-D for the length of the chain.

Individual parameters are updated by Metropolis Hastings (or Gibbs sampling where possible), using only the y_i and y_{it} data available at the time of the update.

2.4 Quantities of Interest

We define a minimally effective dose (MED), a maximum effective dose, and an 85% effective dose. The minimally effective dose ($MED_{\Delta=-0.3}$) is the smallest dose that achieves at least a difference of $\Delta = -0.3$ relative to control. The maximum effective dose (d_{max}) is the dose with the greatest treatment effect (difference from control). The ED85 is the 85% effective dose, or the smallest dose that achieves at least 85% of the treatment effect (relative to control) achieved by the maximally effective dose, d_{max} . For each dose, $d = 1, \dots, 6$, we calculate the probability it is the $MED_{\Delta=-0.3}$, the d_{max} , and the ED85

We define a number of additional quantities from the posterior distributions that will be used to make decisions during the trial. These include

- the probability that the mean response on dose d is less than on control:

$$\Pr(\mu_d < \mu_0) \text{ for } d = 1, \dots, 6$$

- the probability that the mean response on dose d is less than on control by at least -0.3:

$$\Pr(\mu_d - \mu_0 < -0.3)$$

2.5 Conventions for Missing Data

At any analysis, some subjects may have missing data for the final endpoint. The missing data could result from the subject dropping out of the trial, or because the subject simply has not yet reached the final visit.

If the subject has not yet reached the final visit, but has data from an intermediate visit then the missing endpoint is "imputed" from the longitudinal model. This is described in section 2.2. We impute the final 12-week average change from baseline from the most recently observed average change from baseline at an intermediate visit. Multiple imputation involves sampling, in each MCMC iteration, from the posterior estimate of the subject's final endpoint given their intermediate visit data

Trial Code: 000233

and the longitudinal model and the current longitudinal parameters. Thus the imputed value has the uncertainty of the longitudinal model and the estimates of its parameters. If the subject has no interim visit results, the subject's endpoint value is simply imputed from the estimate of the response for the subject's treatment arm (effectively contributing no information to the update of that estimate).

For any subject whose final endpoint is unknown due to drop out, the final outcome will be multiply imputed from the Bayesian model as described above.

3 Trial Design

3.1 Timing of Interim Analyses

The first interim will occur after 125 subjects have enrolled into the trial. This includes 50 subjects to the control (d_0), 50 to the highest dose of FE 201836 (d_6), and 25 subjects on the active comparator (d_{AC}). Subsequent interims will be conducted every 8 weeks and will continue beyond full accrual while the enrolled subjects are completing the 12 weeks of follow-up. Because interims are defined by calendar time, the total number of planned interims, I , is random and will depend on the rate at which subjects accrue to the trial.

3.2 Response Adaptive Randomization

For the initial randomization, 125 subjects will be randomized 4:4:2 to the control, the highest dose of FE 201836 and the active comparator. After this initial randomization, adaptive randomization may begin. During adaptive randomization, subjects will be preferentially allocated to doses most likely to be the MED and ED85. Once adaptive allocation begins, subjects will be randomized in blocks of size 10. Within each block, 2 and 1 subjects will be allocated to control (d_0) and the active comparator (d_{AC}) respectively. The remaining subjects in each block will be allocated adaptively, with allocation probabilities weighted proportional to the probability the dose is the MED and the probability the dose is the ED85. First, we calculate:

$$I_{1,d} = Pr(\text{MED}_{\Delta=0.3} \text{ relative to control}) SE_d^2$$

$$I_{2,d} = Pr(\text{ED}_{85} \text{ relative to control}) SE_d^2$$

where SE_d is the standard error of final endpoint data observed at dose d . The randomization probabilities for the adaptively allocated arms will be updated at each interim. They will be weighted according to

Trial Code: 000233

$$I_{1,d} + I_{2,d}$$

and the weights will be renormalized to sum to 1.

To avoid assigning subjects to a dose with a minimal chance of being the MED or ED85, any probability less than 0.025 is set to zero at that interim and the resulting probability is reallocated among the remaining doses. In this manner, a dose may be temporarily dropped but may be re-introduced if the adaptive randomization probability increases at subsequent interims.

3.3 Criteria for Stopping Early for Futility

At the first interim analysis with 125 subjects enrolled, the trial may stop for futility if there is a low probability that the maximum effective dose achieves a difference of at least 0.3 from control. Formally if

$$\Pr(\mu_d - \mu_0 < -0.3) < 0.1 \text{ for } d = \text{greatest } \Pr(d_{Max})$$

At each subsequent interim analysis, the trial may still stop for futility if there is a low probability that the maximum effective dose achieves a difference of a least 0.3 from control. Formally if

$$\Pr(\mu_d - \mu_0 < -0.3) < 0.05 \text{ for } d = \text{greatest } \Pr(d_{Max})$$

If the futility rule is met at an interim analysis, then subject follow up will be discontinued. The final evaluation criteria of trial success will be applied to the currently available data.

3.4 Final Evaluation Criteria

At the final analysis, the trial will be considered successful if the maximum effective dose achieves a significant difference from control,

$$\Pr(\mu_d < \mu_0) > 0.975 \text{ for } d = \text{greatest } \Pr(d_{Max})$$

3.5 Design Flow Chart

Figure 1 gives a flow chart depicting the overall structure of the design.

[figure not shown]

Figure 1: Flow chart of the design

4 Simulation Scenarios

We evaluate the proposed design through trial simulation. We hypothesize several possible underlying truths for the mean response, the longitudinal nature of the data, as well as for trial execution variables such as accrual and dropout. For each of these scenarios, we generate data according to those truths and conduct the trial design as specified above. We repeat this process to create multiple “virtual trials” and we track the behavior of each trial. In this section, we describe the parameters used to generate the virtual subject-level data.

4.1 Virtual Subject Response Profiles

4.1.1 Final Endpoint Scenarios

We consider 6 scenarios for the final 12-week endpoint values. The null model assumes no dose-response. The other 4 scenarios (I-V), depicted in Figure 2, assume a dose-response all based on a sigmoidal model of different size and shape. Table 1 presents the respective parameter values underlying these scenarios. We evaluate these scenarios assuming the standard deviation of the final 12-week endpoint will be 0.95.

Trial Code: 000233

Table 1: Sigmoidal parameter values and their corresponding ED85 and MED of the different scenarios (note: dose runs from 0 to 5 units)

Scenario	α_2 (max effect)	α_3 (ED50)	α_4	ED85	MED
Null	0	-	-	-	-
I	-0.3	150	4	228	-
II	-0.4	200	4	297	263
III	-0.5	200	4	297	221
IV	-0.5	350	8	417	368
V	-0.6	300	8	368	300

Note : $\alpha_0=0$

[figure not shown]

Figure 2: Mean Dose-Response Scenarios

Trial Code: 000233

4.1.2 Longitudinal Profile

We define a profile for generating the observed data at each earlier visit. Longitudinal data is simulated through the use of subject specific effects. For the i th subject, we simulate a subject effect

$$\delta_i \sim N(0, \tau_d).$$

Then for τ_d (one for each dose d), f_{dt} (one for each dose d and visit t), and ϕ_{dt} , with the constraint that all values are 1 for $t = T$ (the final endpoint time), visits are simulated by computing

$$\kappa_{dt}^2 = \phi_{dt}\sigma_d^2 - f_{dt}^2\tau_d^2$$

and then simulating visits

$$y_{it} \sim N([\theta_d + \delta_i]f_{dt}, \kappa_{dt}^2)$$

The purpose of this structure is to induce correlation through the random effect (interim visits all tend to be higher or lower than the group and arm mean depending on the random effect) while still maintaining a consistent interpretation of the final endpoint variance. Thus, marginally, we find

$$E[y_{it}] = f_{dt}\theta_d$$

and

$$V[y_{it}] = f_{dt}^2\tau_d^2 + \kappa_{dt}^2 = f_{dt}^2\tau_d^2 + \phi_{dt}\sigma_d^2 - f_{dt}^2\tau_d^2 = \phi_{dt}\sigma_d^2$$

so that the f_{dt} terms indicate the proportional value of the mean for the interim visit and the ϕ_{dt} terms indicate the fraction of proportional variance. As these modifiers are constrained to be 1 for the final visit, the interpretation of the final endpoint mean and variance are maintained (and thus the longitudinal model may be turned on and off and produce the same distribution for the final endpoint). We specify the fraction of overall variance that is due to inter-subject variance:

$$\omega_d = \tau_d^2/\sigma_d^2$$

The predictive value of the model occurs due to the correlation between time points, where

$$\text{Corr}(y_{it}, y_{it'}) = \frac{f_{dt}f_{dt'}\omega_d}{\sqrt{\phi_{dt}\phi_{dt'}}} \quad [t \neq t']$$

Trial Code: 000233

The parameter values for f_t and ϕ^2 are shown in Tables 2 and 3. These parameters are based on data observed from previous studies.

Table 2: Response Fraction (f) for the longitudinal profile

Week	f
1	0.8142
4	0.9328
8	0.9874
12	1.0000

Table 3: Fraction of the final variance (ϕ^2) for the longitudinal profile

Week	ϕ^2
1	0.8481
4	0.8329
8	0.8900
12	1.0000

We shall assume that the fraction of the overall variance due to inter-subject variance ω is 0.90

4.2 Accrual Profiles

We simulate the random arrival of subjects into the trial from a Poisson process. We assume accrual will ramp-up linearly for 17 weeks to a peak accrual rate of 8.2 subjects per week.

4.3 Dropout Profiles

We simulate subjects dropping out of the trial. We consider as a scenario in which 15% of subjects on each dose drop out over the course the trial. This is implemented as evenly spaced drop-outs.

5 Operating Characteristics

For the scenarios described above, we simulate 1000 virtual trials and track the behavior of each trial, including the final outcome of the trial, the estimated mean response, etc. The results are summarized across all simulated trials for each scenario.

Table 2 summarizes the trial operating characteristics including the mean sample size, and probabilities of trial success and trial futility. In the null scenario, where the dose-response curve is flat, there is a 3.0% probability of (false-positive) trial success. There is a 75.8% probability that the trial would stop for futility at the first

Trial Code: 000233

interim analysis and a total of a 97.0% probability of total futility, cumulative across all the interim analyses (including failure at the final analysis) .

When the highest dose achieves a mean effect of a 0.5 decrease from baseline, there is a ~85 to 90% probability of trial success.

Trial Code: 000233

Table 2: Operating Characteristics

Dose-Response Scenario	Maximum response (a_2)	ED50 (a_3)	Average Number of Subjects	Futility stopping at 1st Interim	Total Futility stopping	Power (Total Success)
Null	0	0 μg	200	75.8%	97.0%	3.0%
I	-0.3	150 μg	277	15.7%	47.9%	52.1%
II	-0.4	200 μg	288	7.9%	25.1%	74.9%
III	-0.5	200 μg	296	2.8%	9.6%	90.4%
IV	-0.5	350 μg	295	3.4%	15.4%	84.6%
V	-0.6	300 μg	298	1.4%	2.7%	97.3%

Table 3 shows the probability each dose is selected as the MED. The underlying truth is shown in the last column. Neighboring doses to true MED tend to yield the highest selection probabilities.

Table 4 shows the results for the selection of ED85 and in general the results favor the highest dose due to smoothed curvature leading to not enough effect at lower doses (<15% of maximum effect).

Table 3: Probability each dose is selected as the MED

Table 5: Trial Operating Characteristics – Probability Each Dose is Selected as the MED							
Scenario	50 μg	100 μg	150 μg	250 μg	350 μg	500 μg	True MED
N=300							
Null	0.045	0.007	0.001	0.071	0.033	0.843	-
I	0.045	0.047	0.029	0.306	0.057	0.516	-
II	0.024	0.022	0.03	0.372	0.145	0.407	263
III	0.018	0.033	0.043	0.512	0.187	0.207	221
IV	0.008	0.006	0	0.073	0.209	0.704	368
V	0.004	0.004	0	0.19	0.534	0.268	300

Trial Code: 000233

Table 4: Probability each dose is selected as ED85

Table 6: Trial Operating Characteristics - Probability Each Dose is Selected as the ED85							
Scenario	50 µg	100 µg	150 µg	250 µg	350 µg	500 µg	True ED85
N=300							
Null	0.761	0.001	0	0.006	0	0.232	-
I	0.19	0.015	0.008	0.131	0.072	0.584	228
II	0.093	0.007	0.005	0.123	0.139	0.633	297
III	0.036	0.001	0.01	0.172	0.223	0.558	297
IV	0.034	0.001	0.001	0.006	0.019	0.939	417
V	0.015	0	0	0.006	0.081	0.898	368

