4.2.2 Randomisation

A computer-generated randomisation list will be prepared prior to enrolment of the first subject into the trial. The randomisation list will be adjusted during the course of the trial via a response-adaptive randomisation procedure. At least 50% of subjects should be randomised at trial sites in the USA to allow for an optimised validation of the NI Diary. Therefore, a cap of maximum 150 subjects will need to be set for countries other than the USA.

Subject-specific randomisation numbers will be allocated in the order at which the subjects are being randomised into the trial. The subject randomisation number will be recorded in the Screening Log. It is not permitted for a subject to be randomised in the trial twice.

The first 125 subjects will be randomised to treatment in a fixed manner. The allocation ratio is 2:2:1 for placebo, 500 µg FE 201836 and desmopressin. At the first interim analysis, after 125 subjects being randomised, the allocation ratio is 2:7:1 for placebo, active treatment and desmopressin, respectively. Subjects will be randomised to the active treatment groups of FE 201836 in a response-adaptive randomisation manner. A pre-defined algorithm will be used to determine the relative randomisation to each of the FE 201836 groups. Subsequent interim analyses will be conducted every 8 weeks to adjust the adaptive randomisation probabilities. The enrolment of subjects will continue without any stop at the interim analyses. For more information regarding the interim analyses, please refer to Section 3.3 and Section 9.11.

The screening rate will be monitored such that the accrual of randomised subjects does not overshoot the operating characteristics described in Section 9.1, which could potentially result in a loss of statistical power.

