9.11.2 Interim Efficacy Analyses

The planned interim analyses will be conducted by an internal DMC (Section 3.4) according to a separate DMC charter, which will be established before the first interim analysis. The interim analyses will use unblinded efficacy data to infer whether to stop early for futility or to continue the trial as planned.

At the first interim analysis the trial may be stopped due to futility if there is a low probability (less than 10%) that 500 µg FE 201836 is at least 0.3 voids more efficacious than placebo:

$$\Pr(\mu_{MAX} - \mu_{Plb} < -0.3) < 10\%.$$

Up to the first interim analysis (conducted when 125 subjects have been randomised) the allocation ratio is 2:2:1 for placebo, 500 µg FE 201836 and desmopressin. Should the trial continue, the allocation ratios will be changed to 2:7:1, where all doses of FE 201836 (50-500 µg) are opened for response-adaptive allocation. The randomisation probabilities for each dose of FE 201836 will be proportional to the average of $I(\text{dose is MED})$ and $I(\text{dose is ED}_{85})$, where $I(\text{target})$ is the square root of the probability that “dose is target” scaled by the standard error at that dose.

The remaining interim analyses are planned to occur every 8 weeks as depicted in the decision tree (Figure 9-2).

These interim analyses will re-iterate the (overall) futility criteria at the 5% threshold:

$$\Pr(\mu_{MAX} - \mu_{Plb} < -0.3) < 5\% \text{ (see Table 9-2 for interpretation).}$$

At the final analysis (when all subjects have had their 12-week visit, or discontinued prior to this visit) Proof-of-Concept is established if $\Pr(\mu_{MAX} < \mu_{Plb}) > 97.5\%$.

[figure not shown]

Figure 9-2 Interim Analysis Decision Tree (2nd Interim Analysis and Onwards)

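### The stated 75.8% chance of stopping an ineffective drug at the first interim does not follow from the stated rule, SD and arm sizes, which give about 62–65% at best

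*Protocol*

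**What the plan says.** Appendix 2, Section 5 describes the null scenario: "There is a 75.8% probability that the trial would stop for futility at the first" interim analysis, and "a total of a 97.0% probability of total futility, cumulative across all the interim analyses (including failure at the final analysis"). The same column, labelled as futility stopping at the first interim, appears in the Synopsis (Table S-2), Protocol Section 9.1 (Table 9-1), Appendix 2 Section 5 (Table 2) and SAP Section 3.1.2 (Table 2). It reads 75.8, 15.7, 7.9, 2.8, 3.4 and 1.4% for the null and Scenarios I–V.

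The design behind these figures is also stated:

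- **Rule** (Appendix 2, Section 3.3; Protocol Section 9.11.2): "At the first interim analysis with 125 subjects enrolled, the trial may stop for futility if there is a low probability" of a 0.3-void advantage over placebo, the cut-off being a posterior probability of 10%.
- **Arm sizes** (Appendix 2, Section 3.1): "This includes 50 subjects to the control", 50 to 500 µg and 25 to desmopressin.
- **Variability** (Appendix 2, Section 4.1.1): "We evaluate these scenarios assuming the standard deviation of the final 12-week endpoint will be 0.95".
- **Accrual** (Appendix 2, Section 4.2): "We assume accrual will ramp-up linearly for 17 weeks to a peak accrual rate of 8.2 subjects per week".
- **Model**: wide priors (Appendix 2, Section 2.1), no baseline adjustment in the simulations, and 1,000 simulated trials per scenario.

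**The concern.** A futility rule on one contrast, with known arm sizes and SD and weak priors, has a stop rate that can be worked out almost by hand. The stated null figure is well above what those inputs allow even if every subject had final data.

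The first look is the gate of the top-down design: if it is passed, all lower doses open. The column is the only published measure of how well that gate holds back an ineffective drug. The total-futility column cannot stand in for it, because it counts failure at the final analysis and therefore sums with power to 100.0% in all six rows.

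**Working it through.** **1. Null row, complete data, flat prior.**

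SE of the difference = 0.95 × √(2/50) = 0.19. The trial stops when the observed difference lies above -0.3 + 1.2816 × 0.19 = -0.0565. So

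P(stop) = Φ((effect + 0.3)/SE − 1.2816).

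Null: Φ(0.3/0.19 − 1.2816) = Φ(0.297) = **61.7%**, against 75.8% stated. The simulation SE of the stated figure is √(0.758 × 0.242/1000) = 1.35 points, so the gap is (75.8 − 61.7)/1.35 ≈ 10 SEs.

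**2. Stated Emax priors, complete data.**

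Four simulations gave 62.1, 62.9, 63.9 and about 65%. The highest two estimated the variance. Three of the four, including those two, applied the rule to the dose most likely to have the maximum effect. None approaches 75.8%.

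**3. What 75.8% would need.**

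Φ⁻¹(0.758) = 0.700, so 0.3/SE = 0.700 + 1.2816 = 1.982 and SE = 0.151. That means one of:

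- about 79 complete subjects per arm;
- an SD of about 0.76 with 50 per arm;
- a cut-off of about 19% instead of 10%.

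Other readings at the 10% cut-off also miss: 62.5 per arm 68.6%; Week 1 variance 66.8%; Week 4 variance 67.3%; between-subject SD only 64.9%. A 20% cut-off gives 77.0%, but it contradicts the rule and would stop about 20% in Scenario I.

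**4. All rows.**

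True effects at 500 µg come from the sigmoid parameters in Appendix 2, Section 4.1.1. Example, Scenario I: -0.3 × 5⁴/(5⁴ + 1.5⁴) = -0.298.

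| Scenario | True effect at 500 µg | Stated % | Closed form % | Emax priors, known SD % | Emax priors, estimated variance % | Stated minus closed form, in SEs |
|---|---|---|---|---|---|---|
| Null | 0 | 75.8 | 61.7 | 62.9 | about 65 | 10.4 |
| I | -0.298 | 15.7 | 10.2 | 10.5 | 10.4 | 4.8 |
| II | -0.390 | 7.9 | 4.0 | 4.6 | 3.9 | 4.6 |
| III | -0.488 | 2.8 | 1.2 | 1.2 | 1.3 | 3.1 |
| IV | -0.473 | 3.4 | 1.4 | 1.3 | 1.5 | 3.5 |
| V | -0.590 | 1.4 | 0.25 | 0.3 | 0.3 | 3.1 |

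Scenario I sits almost on the margin. With a flat prior, a 10% rule stops about 10% of such trials whatever the sample size, so a larger effective n could lift the null row but not this one.

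**5. Stated follow-up (indicative).**

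The ramp enrols 8.2 × 17/2 = 69.7 subjects by week 17. The 125th arrives at about week 17 + (125 − 69.7)/8.2 = 23.7. Those enrolled at least 12 weeks earlier, by week 11.7, number (8.2/17) × 11.7²/2 ≈ 33. The other final values are imputed, so the SE exceeds 0.19 and the null stop rate falls. Four approximate runs with the stated accrual, visit profile and dropout gave 50.8, about 53, 55.6 and 59.6%.

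**6. Average N (conditional).**

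If a stop counts 125 subjects, the null average cannot exceed 0.758 × 125 + 0.242 × 300 = 167; the table says 200. This fails as proof if subjects enrolled during the interim are counted.

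**The case against.** The strongest reply is that the original simulator and its settings are not in the documents, and every simulation here approximates it. That weakens the partial-follow-up figures, which spread over about nine points according to modelling choices; only their direction is useful. It does not weaken the complete-data result, which is closed form and changes little under the stated priors, an estimated variance or the maximum-effect-dose rule.

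Scenario I is less decisive alone than the closed form suggests. Complete-data runs with Emax priors ranged from 10.4 to 12.9%, and against 12.9% the stated 15.7% is only about 2 SEs away. It supports the null row rather than being a second proof.

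The average-N check proves nothing by itself: Protocol Section 4.2.2 says "The enrolment of subjects will continue without any stop at the interim analyses", so overrun could explain it. Overrun adds no data to the first-look rule, however, and cannot explain the stop rates.

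The column might instead hold stops at any interim. Approximate runs over all looks gave 78–81% for the null and 12–15% for Scenario I, near the table, but 4.9–5.9, 1.6–1.8, 1.9 and 0.5% for Scenarios II–V, all below it. This is a possibility only, and the text of Appendix 2 names the first interim explicitly.

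The consequence is also bounded. Later looks repeat the futility test, and success rests on the final 97.5% criterion.

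**Conclusion.** The concern holds. On the stated inputs the null probability of stopping at the first interim is 61.7% in closed form and 62–65% with the stated priors, assuming complete data on 50 per arm. The stated 75.8% is about 11 to 14 points too high. The stated follow-up lowers the rate, to roughly 50–60% in approximate runs. An ineffective drug would therefore pass the gate about 35–38% of the time with complete data, and about 40–50% on the indicative runs, rather than the 24% implied. Scenarios I–V point the same way.

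Confidence is high for the null row on complete data and lower for the other figures. The cause cannot be found from the documents. Nothing here shows that power, the 3.0% false-positive rate, total futility or average N is wrong.

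**What to change.** Check the existing simulation output for the first-interim column, and re-run it if the output does not settle the matter. Then:

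- correct or relabel the column in Protocol Tables S-2 and 9-1, Appendix 2 Section 5 Table 2 and SAP Table 2, and correct the sentence in Appendix 2, Section 5;
- report first-interim stops, stops at any interim and final-analysis failures as separate columns;
- state whether average N includes subjects enrolled while an interim is being run.

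Change the average-N, total-futility and power columns only if the check shows that they differ. The cost is a look at existing output, at most one re-run, and edits to four tables and one sentence. No threshold or trial conduct changes.
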